As with any product, there is a risk that unanticipated effects from using the e-cigarette may occur. The risk however of using the product as directed by the manufacturer is no higher than it would be if subjects were to buy the e-cigarettes themselves and use them outside of the study.

- 11.2 Reproduction Risks: Smoking cigarettes during pregnancy is known to be harmful to reproductive health. We will therefore exclude women who are pregnant or are planning to become pregnant during the study. Women who inform us that they have become pregnant during the study will not be provided any additional tobacco products.

PROTOCOL TITLE: Menthol Flavored E-Cigarette Use During a Simulated Ban of Menthol Cigarettes

VERSION DATE: 10/14/2019

11.3 Risks to Others: There are known risks associated with second hand smoke, however we are only recruiting those who are already smoking therefore the risk to others should not increase by participating in this study. The second hand risks of e-cigarette use are unknown but are likely less than the risks of second hand smoke.

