Subjects: In order to be eligible for this study, subjects must: 1) be African American (based on self-identification); 2) smoke primarily menthol cigarettes (greater than 80% of products used are menthol); 3) be between the ages of 18 and 64; 4) Smoke on average at least 5 cigarettes per day for a period longer than 1 year; and 5) agree to abstain from menthol cigarettes for an 8 week period. Subjects will be excluded if they have: 1) a current serious, unstable medical or psychiatric condition as determined by self-report; 2) Regularly use any form of nicotine or tobacco other than cigarettes (i.e. greater than 9 times per month); or 3) Are pregnant or breast feeding based on self-report (subjects will be given a urine pregnancy test at the screening visit with pregnancy later in the study and breast feeding based on self-report). Regular users of e-cigarettes will be excluded as they likely have identified a preferred flavor.

As the risks associated with the study procedures are small, all medical assessments are based on self-report (except for a urine pregnancy test at screening).

Recruitment will be limited to African American smokers since menthol cigarette use is particularly prevalent in this community³ and because data suggest that greater difficulty in cessation of menthol (vs. non-menthol) cigarettes may be limited to African Americans.³ Regulation of menthol in non-cigarette tobacco products (such as e-cigarettes) may therefore be particularly relevant to this population.

African American menthol smokers will be recruited via the use of flyers and advertisements in local and neighborhood newspapers with a high African American readership or on internet resources such as Craigslist or Facebook. If additional advertisement becomes necessary, radio or television advertisements may be utilized.

Implementation Plan

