Overview: Each subject will attend a screening visit to determine eligibility for the study. If subjects are eligible, they will be scheduled to attend a baseline visit until which they will be asked to continue smoking in their normal manner in order to gather information on their baseline smoking patterns. At the baseline visit, subjects will be randomized to either the 'simulated menthol cigarette ban' or 'no menthol cigarette ban' conditions and additionally will be randomized to the order in which they will receive their assigned e-cigarettes (i.e., menthol flavored e-cigarettes followed by non-menthol tobacco flavored e-cigarette or vice versa). Based on their randomization, subjects will be instructed

as to whether they are to abstain from menthol cigarettes and will be provided a supply of e-cigarettes in the flavor they were randomized to for the first 4 week period. Subjects will be seen at visits scheduled approximately two and four weeks after starting use of their assigned e-cigarettes and will receive a phone call one week after starting use of their e-cigarettes to address any questions that arise. At the week four visit, subjects will receive a supply of the alternate e-cigarette products that they will use for the subsequent four week period. We do not believe that a washout period is needed based on a published cross-over study in which differences were found between menthol and tobacco flavored e-cigarettes after each was used for only a 7 to 10 day period (with no wash-out in between).²² During the second four week period, subjects will again receive a phone call 1 week after starting use of their assigned e-cigarette product and will be seen at visits scheduled two and four week after starting use of their assigned product. In order to ascertain if subjects change their tobacco use behavior once e-cigarettes are no longer provided by the study, subjects will have an additional follow-up visit 12 weeks after the baseline visit (i.e., four weeks after the end of the second assessment period). Subjects who complete the entire study will therefore be seen at a screening visit and 6 additional visits over an approximately 3 month period. The procedures occurring during each of these visits are described below.

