To the baseline visit, subjects will bring a first morning urine sample from which baseline urinary cotinine and total NNAL concentrations will be measured. Exhaled CO will be measured from a breath sample. Tobacco use behavior subsequent to the screening visit will be determined as will subjects' level of craving, withdrawal, motivation, self-efficacy to quit smoking, and support for a ban on a variety of menthol containing tobacco products. Subjects will then be told if they have been assigned to the condition in which they are to abstain from menthol cigarettes for the next eight weeks and will be provided (at no cost to them) with a two weeks supply of the product that they have been randomized to receive (i.e., menthol or tobacco flavored e-cigarettes, based on randomization) for the first four week period. Subjects will be instructed in how to properly use the product and will be given all of the packaging that normally accompanies the product. They will be told to use as much or as little of the product as they like. Subjects will also be provided with a tobacco use diary that they are to complete daily in which they are to record the number of cigarettes smoked and how often and how many puffs they used of their provided e-cigarette. Puffs per day has been used in other studies to evaluate e-cigarette use.^{22, 30, 31} They will additionally be asked to record use of any other tobacco or nicotine containing products. Subjects will also be asked to bring to all subsequent visits all e-cigarette cartridges as well as samples of the cigarettes or other tobacco or nicotine products that

they have been using in order to verify the accuracy of the smoking diary. Partially used cartridges will be weighed to determine the extent to which they were used. They will be given no specific instructions regarding using medicinal nicotine (i.e., nicotine patch, gum) or other tobacco products but will be asked to record any instances of using such products.

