Evaluation visits will occur at approximately 2 week intervals for eight weeks following the baseline visit. Scheduling considerations will determine the exact intervals of the visits with visits scheduled as close as possible to dates corresponding to those that would occur 2 and 4 weeks after the baseline visit and then 2 and 4 weeks after the week 4 visit (i.e., 2 and 4 weeks after they receive the alternate e-cigarette product). At the week 2 and week 6 visits, subjects will be told that they have 24 points that are worth \$1.00 per point, which they can exchange for cash or additional e-cigarette cartridges of their assigned flavor (at a cost of 3 points per cartridge, which is approximately 66% of the cost of the cartridges commercially). This approach is being used in order to better characterize how menthol vs. tobacco flavored e-cigarettes are likely to be used after subjects have become familiar with the product over the first two weeks. Providing free product for the entire four week period may result in participants using more of the product than they would otherwise use and smoke fewer cigarettes since the e-cigarettes are free and the cigarettes are not. Differences between menthol and non-menthol e-cigarette conditions may therefore be underestimated in this circumstance. Products are offered at a discount to the price available in the retail marketplace in order to ensure that any cartridges are obtained from us (rather than commercially) but to minimize hoarding of the points.

At each visit, exhaled carbon monoxide concentrations will be measured and subjects will complete questionnaires assessing craving and withdrawal symptoms, motivation to quit smoking, product liking, perceived health risks of using the product, and level of support for a ban on a variety of menthol containing tobacco products. The tobacco use diaries that subjects had been asked to complete will be collected at each visit.

At the week 4 and week 8 visits, subjects will be asked to bring a urine sample with their first morning void which will be used to measure urinary cotinine and urinary total NNAL concentrations.

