To ensure confidentiality, all subjects enrolled in the study will be assigned a study identification code which will be used on all study related data collection forms except for those on which the use of personal identifiers is mandatory (e.g., informed consent form). Forms that link the name of the participant and the subject identification code will be kept in a locked cabinet or office or in an electronic file stored on password protected secure computer servers that meet university guidelines. Access to subject identifiable information will be limited to those that require this information such as investigators or others who have direct contact with study subjects (e.g., study coordinator).

At each visit, subjects will be asked if they are experiencing any adverse effects or difficulties with the study. The Principal Investigator will review reports with study staff to determine if changes are needed to any of the study related procedures or if the subject has symptoms/difficulties that would warrant discontinuation from the study.

Data Analysis

The primary aim of the proposed study is to compare changes in each outcome measure (e.g., number of cigarettes smoked, amount of e-cigarette used, motivation to quit smoking, biomarker concentrations, support for a menthol ban) between the four week period when subjects are provided menthol e-cigarettes compared with the four week period when subjects are provided tobacco flavored e-cigarettes. An additional aim is to determine if cigarette type (i.e., randomization to menthol vs non-menthol) moderates the effects of e-cigarette type.

Outcomes will be described using means and standard deviations, separately for each combination of visit and experimental condition (menthol cigarettes available or not, menthol or non-menthol tobacco flavored e-cigarette). Skewed variables will be log transformed and their geometric means and 95% confidence intervals will be reported. Hypothesis testing will be performed using linear mixed models, with fixed effects for randomization group and time, and a random subject effect. The study is designed to provide pilot data to estimate broad trends and parameters that can be used

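### After screening, no listed visit procedure asks about pregnancy, so the rule that stops product supply works only if a woman volunteers it

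*Combined protocol and SAP*

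**What the plan says.** Three statements in the combined document govern pregnancy after enrolment.

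- The eligibility text (Research Design and Methods, Subjects) provides one test and then self-report: "subjects will be given a urine pregnancy test at the screening visit with pregnancy later in the study and breast feeding based on self-report".
- Section 11.2 (Reproduction Risks) excludes women who are pregnant or planning pregnancy, then sets the stopping rule: "Women who inform us that they have become pregnant during the study will not be provided any additional tobacco products".
- The Data and Safety Monitoring Plan has the only health question put at every visit: "At each visit, subjects will be asked if they are experiencing any adverse effects or difficulties with the study". The Principal Investigator reviews what is reported.

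Product is made available at four visits.

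- At baseline, participants "will be provided (at no cost to them) with a two weeks supply of the product".
- For the crossover: "At the week four visit, subjects will receive a supply of the alternate e-cigarette products".
- In the second half of each period: "At the week 2 and week 6 visits, subjects will be told that they have 24 points". Points can be taken as cash or spent on cartridges at 3 points each.

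**The concern.** The protocol has already decided that a pregnant participant should get no more study product. That decision takes effect only when staff learn of the pregnancy, and the listed procedures never have staff ask. An uncomplicated pregnancy is neither an adverse effect nor a difficulty with the study, so the every-visit question does not call for it to be mentioned. Staff could follow the procedures exactly, receive a truthful no, and hand over product that section 11.2 says should be withheld.

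At stake is study-supplied nicotine product reaching a woman who knows or suspects she is pregnant. This is a participant-safety point. It has no bearing on power, the crossover comparison or any outcome measure.

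**Working it through.** The plan gives no figure on this point to reproduce. The check has two parts: whether any listed contact asks about pregnancy, and how much supply could follow if none does.

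**Contacts after the screening test**

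| Contact (where described) | Listed content, in summary | Pregnancy item |
|---|---|---|
| Baseline (Baseline and Evaluation Visits) | urine for cotinine and NNAL, CO, tobacco use, questionnaires, first supply | none |
| Phone call one week into each period (Implementation Plan, Overview) | answering participants' questions | none |
| Weeks 2, 4, 6 and 8 (Baseline and Evaluation Visits) | CO, questionnaires, diaries; urine at weeks 4 and 8 for cotinine and NNAL | none |
| Week 12 (Follow up visit) | urine, CO, diaries, questionnaires | none |
| Every visit (Data and Safety Monitoring Plan) | general question on adverse effects or difficulties | not named |

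The evaluation-visit list opens "At each visit, exhaled carbon monoxide concentrations will be measured and subjects will complete questionnaires assessing craving and withdrawal symptoms" and continues with motivation to quit, product liking, perceived risk and views on a ban. Pregnancy is not among its items. Section 10.1 allows withdrawal for health changes likely to affect smoking, but that also requires staff to know of the change.

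**Supply that could follow**

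Inputs: supply at weeks 0 (baseline), 2, 4 and 6; supply ends at week 8; 24 points at each of weeks 2 and 6; 3 points per cartridge.

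For a woman who first knows or suspects at week *w*, and counting supply at that visit:

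- supply points left = the number of visits among weeks 0, 2, 4 and 6 that fall at or after *w*
- maximum weeks of supply left = 8 − *w*
- cartridges obtainable with points = (24 / 3) × exchange visits left = 8 × exchange visits left

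| First knows or suspects at | Supply points left | Weeks left | Cartridges obtainable with points |
|---|---|---|---|
| Baseline | 4 | 8 − 0 = 8 | 8 × 2 = 16 |
| Week 2 | 3 | 8 − 2 = 6 | 8 × 2 = 16 |
| Week 4 | 2 | 8 − 4 = 4 | 8 × 1 = 8 |
| Week 6 | 1 | 8 − 6 = 2 | 8 × 1 = 8 |
| Week 8 | 0 | 0 | 0 |

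The cartridges obtained with points come on top of any free supply still due at baseline and week 4. Supply points with a listed pregnancy question: 0 of 4. All figures are ceilings, since points may be taken as cash and visit dates are approximate.

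**The case against.** The strongest reply is that this is a stated and reasoned choice. The Subjects section says that, because the procedures carry little risk, medical assessments rest on self-report, with the screening pregnancy test as the one exception. Self-report can include staff eliciting the answer, and the visit descriptions are prose summaries, not forms. A pregnancy item or an instruction to report could sit in the visit forms, the consent pages or the initially approved IRB application, none of which is in the file. The population at risk is also narrow: section 11.2 excludes women planning pregnancy, and everyone has a test at screening. The four-point maximum needs a negative test followed by knowledge or suspicion by baseline, and two of the four supplies are optional. Finally, all participants already smoke at least 5 cigarettes per day, so withholding cartridges would not stop the smoking.

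Much of this stands as a limit on size. The benefit is modest, the maximum is an edge case, and unseen forms may already contain the question. It does not remove the gap. The protocol describes a passive trigger, and no listed procedure supplies a prompt. The self-report design is not in dispute; what is missing is a scheduled occasion for the report. That participants smoke anyway is an argument against having the stopping rule at all, and the protocol chose to have it. The general question and the phone calls may prompt disclosure, but neither asks for it.

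**Conclusion.** The concern holds for the procedures as written. Section 11.2 has a stop-supply rule with no scheduled question to trigger it. A woman who knows or suspects she is pregnant and does not say so could be supplied at up to four points, for at most about 8 weeks.

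This rests on three conditions: no pregnancy question exists in the forms or consent material that could not be seen; the woman has no complaint that would bring the pregnancy up under the general question; and, for the maximum, she first knows or suspects by baseline after a negative screening test. The documents give neither the number of women nor a pregnancy rate, so no expected number of cases can be stated.

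The change should be made because it is cheap and serves a rule the protocol already contains. It is not a reason to hold the trial, and no endpoint, analysis or sample size is affected.

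**What to change.** In the Data and Safety Monitoring Plan, add a step at baseline and weeks 2, 4 and 6: before product is handed over or points are exchanged, staff ask each woman directly whether she is or may be pregnant and record the answer. A yes triggers section 11.2. A may-be goes to the Principal Investigator review already described there, before any product is given; the amendment should say how that review decides.

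Reword section 11.2 so that it covers a pregnancy reported either in answer to this question or at any other time. The Subjects section can stay as it is: self-report after screening, with no further test.

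The cost is one question at each of four existing visits and a short wording amendment. If staff already ask, the amendment only documents the practice. It will not find an unrecognised pregnancy, nor one that a participant chooses not to disclose.

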to plan larger studies. Enrolling a total of 40 subjects with 15-20% attrition would leave at least 16 subjects per group to compare menthol vs. no menthol cigarettes allowed, and those 16 can be compared within each group to test the effects of e-cigarette flavor since all subjects will receive both flavor options in a crossover design. This would result in approximately 80% power to conclude significance at the two sided 0.05 level if the true effect size is 1.0.

The results of this study will be used to plan future projects that would more definitively address the question of how menthol flavoring in e-cigarettes should be regulated. This formative study would inform future research by 1) demonstrating the acceptability of menthol and non-menthol flavored e-cigarette use in this population; 2) providing pilot data regarding how menthol flavoring in e-cigarettes affects (in the presence and absence of a simulated ban on menthol cigarettes) smoking changes, thereby enabling more informed hypotheses to be developed and more accurate sample size calculations to be performed and 3) providing information for study design refinement via the descriptive data collected from participants regarding their recommendations for future study designs.

Data and Record Keeping:

Data will be managed by the study coordinator(s). To ensure confidentiality, all subjects will be assigned a study identification code to be used on all data collection forms except those for which use of personal identifiers is mandatory (e.g., informed consent form). Forms that link the name of the participant and the subject identification code will be kept in a locked cabinet or office or in an electronic file stored on password protected secure computer servers. Access to subject identifiable information will be limited to those that require this information such as study investigators or others who have direct contact with study subjects (e.g., study coordinator).

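### As literally written, the only hypothesis-testing model contains neither the flavor contrast nor its moderation by the ban, unless the undefined 'randomization group' is read as the ban-by-flavor condition or an unlisted interaction is added

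*Combined protocol and SAP*

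**What the plan says.** All inferential text is in the Data Analysis section of the protocol. The primary aim compares each outcome "between the four week period when subjects are provided menthol e-cigarettes compared with the four week period when subjects are provided tobacco flavored e-cigarettes". The second aim is moderation: "An additional aim is to determine if cigarette type (i.e., randomization to menthol vs non-menthol) moderates the effects of e-cigarette type". Specific Aims/Study Objectives states the same two questions as Aims 1 and 2.

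Descriptive summaries are to be given "separately for each combination of visit and experimental condition (menthol cigarettes available or not, menthol or non-menthol tobacco flavored e-cigarette" (that is, by visit within the four ban-by-flavor combinations, which this sentence calls the experimental condition). The model sentence comes shortly afterwards and uses a different term: "Hypothesis testing will be performed using linear mixed models, with fixed effects for randomization group and time, and a random subject effect". It names no flavor, period or order term and no interaction.

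The sample-size text in the same section uses 'group' for the ban arm: "at least 16 subjects per group to compare menthol vs. no menthol cigarettes allowed". It adds that "those 16 can be compared within each group to test the effects of e-cigarette flavor", because every subject receives both flavors.

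The Implementation Plan overview describes two randomizations at baseline. Subjects are allocated to ban or no ban, and they "additionally will be randomized to the order in which they will receive their assigned e-cigarettes". The same overview also describes flavor itself as randomized, since subjects receive "e-cigarettes in the flavor they were randomized to for the first 4 week period".

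**The concern.** Flavor is a within-subject factor that switches at week 4. A model can test it only if it has a term that switches with it. 'Randomization group' could mean three things in these documents:

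- **(a) The ban arm.** This is the nearest usage: the sample-size text uses 'group' this way, and the moderation aim uses 'randomization' for cigarette type.
- **(b) The ban-by-order cell.** These four cells are what a subject is actually allocated to at baseline.
- **(c) The ban-by-flavor condition in force at each visit.** The descriptive sentence defines this set of four, and the overview's wording about flavor being randomized lends it some support.

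Readings (a) and (b) are fixed for a subject throughout the study; only (c) changes when the flavor changes. An analyst who fits the listed terms under (a) or (b) obtains no test of either aim.

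A second question arises even under (c). Most outcomes are measured at two visits in each flavor period. A single random subject effect treats those two visits as independent given the subject, so it ignores any tendency of a subject to run high or low for a whole period.

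**Working it through.** **The plan's own power figure.** Inputs from the sample-size text: 40 enrolled, up to 20% attrition, effect size 1.0, two-sided 0.05. Completers: 40 × 0.80 = 32, or 16 per ban arm. Two-sample normal approximation: 1.0 × √(16/2) = 2.83; 2.83 − 1.96 = 0.87; power 80.7%. The t version gives 78.1%. The stated figure of about 80% is reproduced and is not in dispute. A paired t-test on 16 subjects, with the effect in SDs of the differences, would give 96.2%, so the stated figure corresponds to a comparison of 16 with 16.

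**What each reading can test.** Write the fitted mean as a group term plus a visit term, and take menthol minus tobacco within a period, averaged over the two periods, in one arm.

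- (a) Ban arm + visit: both orders in the arm have the same fitted value at each visit, so the difference is 0.
- (b) Cell + visit: let g1 be the menthol-first cell and g2 the tobacco-first cell. Period 1 gives g1 − g2 and period 2 gives g2 − g1. The average is 0 whatever the data.
- (c) Ban-by-flavor condition + visit: the difference is the menthol condition term minus the tobacco condition term, free in each arm.

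Noise-free refit, with arbitrary flavor effects of 1.0 (no ban) and 2.0 (ban):

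| Fixed effects | No ban | Ban |
|---|---|---|
| Ban arm + visit | 0.0 | 0.0 |
| Ban-by-order cell + visit | 0.0 | 0.0 |
| Ban-by-flavor condition + visit | 1.0 | 2.0 |
| Flavor × ban + visit | 1.0 | 2.0 |
| Cell × visit (interaction not listed in the plan) | 1.0 | 2.0 |

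Results are the same for weeks 2, 4, 6 and 8 and for weeks 4 and 8 only, and for completers of 8 per cell or 9/7 (no ban) and 6/10 (ban). A rank check that adds baseline and week 12 gives the same answer. Ban arm × visit still contains neither contrast.

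Simulation agrees (4,000 crossovers, 8 per cell, subject and residual variance assumed 0.5 each). Under a 1.0 SD flavor effect, or a 1.0 SD difference in flavor effects between arms, the group test under (a) or (b) rejects 3.9% to 5.2% of the time, about the nominal level. Under (c) the relevant test rejects about 100% and 98%. Those two powers depend on the assumed variances.

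**Random-effect check, under (c), with no flavor effect.** 32 completers, two visits per period, residual variance 1. Let r be subject-by-period variance divided by residual variance. The documents give no variance components, so r is assumed.

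- A subject's difference between period means has variance 2(r + 1/2) = 1 + 2r.
- The subject-only model has 128 − 32 − 3 − 2 = 91 residual df. Of these, 32 − 3 = 29 carry mean square 1 + 2r and 62 carry mean square 1. It therefore uses [29(1 + 2r) + 62]/91 in place of 1 + 2r.
- Approximate type I error: two-sided t tail (91 df) beyond 1.986 ÷ √(true variance ÷ variance used).

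| r | True | Used | Ratio | Approx. type I error | Simulated (20,000 runs) |
|---|---|---|---|---|---|
| 0 | 1.0 | 1.000 | 1.000 | 0.050 | 0.050 |
| 0.25 | 1.5 | 1.159 | 1.294 | 0.084 | 0.086 |
| 0.5 | 2.0 | 1.319 | 1.517 | 0.110 | 0.109 |
| 1.0 | 3.0 | 1.637 | 1.832 | 0.146 | 0.146 |

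Simulated flavor-by-ban errors are 0.048, 0.086, 0.109 and 0.144. With one value per period (29 df) the flavor error stays at 0.049 to 0.051. Mean 95% half-widths for flavor are then 0.358, 0.439, 0.507 and 0.622, against 0.350, 0.377, 0.402 and 0.448 for the subject-only model: 2%, 16%, 26% and 39% wider.

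**The case against.** The strongest reply is that the intent is plain. The same section makes flavor the primary comparison and ban moderation the second, defines the ban-by-flavor conditions just before the model, and says flavor will be compared within each arm. An analyst would have to overlook the stated aims to fit (a) or (b). This stands. A reader might infer that the trial will not test its own aims, or that the sponsor chose a wrong analysis; the documents do not support that. The zeros above follow by construction from leaving flavor out. They show what a reading can test, not which reading is meant.

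The model sentence also neither lists nor excludes an interaction. If it is shorthand for group by time under (b), both aims are testable, because flavor is determined by order and period. So it would be too strong to say that only the ban-by-flavor reading works. That interaction is not written, however, and under the nearest reading, (a), adding it would not help.

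The random-effect point is a separate matter and conditional. It needs nonzero subject-by-period variance, which the documents do not quantify, and two visits per period in the model, which the plan does not specify. Urinary cotinine and NNAL are collected once per flavor period, at weeks 4 and 8, and are unaffected. It would be wrong to infer that all tests in this trial are liberal.

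Finally, this is a declared pilot meant to estimate broad trends, and the visit-by-condition means give point estimates under any reading. That limits the harm. It does not remove it: the plan commits to hypothesis tests and quotes power at two-sided 0.05, and the flavor contrasts and their standard errors are what a larger study would be planned from.

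**Conclusion.** The point holds in a limited form and should be fixed. With the listed main effects and no interaction, the only inferential model contains neither the flavor nor the flavor-by-ban contrast if 'randomization group' means the ban arm or the ban-by-order cell. It contains both if the term means the time-varying ban-by-flavor condition, or if a cell-by-time interaction is added. This part is algebra and needs no assumption about variances or completer numbers. The aims themselves are clear, and the model sentence should be made to match them.

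The second part is conditional. Where two visits per flavor period are analyzed, the single subject effect gives type I error of 0.05 if r is 0 and about 0.08 to 0.15 for assumed r of 0.25 to 1.0, with 32 completers.

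**What to change.** Replace the model sentence with wording to this effect: a linear mixed model on the on-treatment visits (weeks 2, 4, 6 and 8; weeks 4 and 8 for urine biomarkers), with fixed effects for e-cigarette flavor, ban arm, flavor-by-ban and visit, and a random subject effect. Where there are two visits per period, add a random subject-by-period effect, or analyze one prespecified value per period, such as the period mean or the week 4 and week 8 value. For the fixed effects it is equivalent to define 'randomization group' as the ban-by-flavor condition in force at each visit.

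Name the flavor contrast averaged over the two arms as the Aim 1 test and the flavor-by-ban term as the Aim 2 test.

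One choice should be made knowingly. The visit term adjusts mean levels only, so using all four visits pools the flavor effect over the weeks when product is supplied free and the weeks when it is bought with points. Using the week 4 and week 8 values would confine the effect to the latter.

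The cost is one or two sentences and a few degrees of freedom, with no new data, visits or subjects. Intervals widen if subject-by-period variance is present (16% to 39% for assumed r of 0.25 to 1.0); that width reflects variation the subject-only model leaves out.
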